## **Statistical Analysis Plan (SAP)**

The statistical considerations for analyzing the data collected in the study are detailed below:

First, analyses will be carried out with the SPSS 26.0 version (IBM, SPSS, 2019).

Descriptive statistics (means, standard deviations, and percentages) of all the sociodemographic, clinical, and psychological variables will be calculated. A Shapiro–Wilk test will be used to check normal distribution.

Participant BMI changes over time by group will be measured using a Kruskal-Wallis test.

To carry out the comparisons, two-way analysis of covariance (ENTREN-F, ENTREN, Control Group) and time (T0,T1, T2 and T3) will be used.

Mixed model repeated measures analyses of covariance models tested whether intervention effects varied for each type of group.

In those cases in which we found significance in the global comparisons, we will carried out pairwise comparisons following asignificant main effect of time (post hoc Bonferroni test).

Finally, the effect size will be measured using partial eta squared ( $\eta$ 2), which estimates the degree of association for the sample. The guidelines for interpreting this value are as follows:  $\geq$ 0.14, large effect;  $\geq$ 0.06, medium effect;  $\geq$ 0.01, small effect (Cohen, 1988). The value P<0.05 was considered as a significant difference.

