The specific hypotheses of the present study were as follows: (a) There will be significant differences in the adherence to treatment, being higher in the ENTREN-F group (b) There will be improvements in clinical outcomes regarding the anthropometric variables of the child, the level of physical activity, psychological distress, and eating disorder of the child, after both interventions (ENTREN and ENTREN-F programme), in comparison to control group (d) There will be only improvements in clinical outcomes regarding in the family's healthy life-style, psychological distress of the parents, and the family environment, after the intervention of the ENTREN-F programme. (e) The significant changes produced will remain stable at the 6, 12 and 18-month follow-up in the ENTREN-F group.

Method

Participants and Recruitment Procedure

The sample will be made up of 240 children of 8-12 years old (IMC>P90). The dropout rate is expected to be 20%. The majority of the participants will be recruited through Primary Health Care Services, in collaboration with Pediatrics Area. Another percentage of the sample contacted the program after receiving information from their school or advertising posters.

Participation was voluntary and informed assent and consent was obtained by each participating family. Participants were told that the personal content of session discussions was confidential and should not be discussed outside the sessions.

Participants were randomly assigned to either (a) the psychofamily-based workshop program (ENTREN-F), (b) the only psychological workshop program (ENTREN) or (c) the Control Group. Participants were asked to complete questionnaires at baseline prior to the intervention (T_0) , at the end of the intervention and (T_1) , at 6-month follow-up (T_2) , at 12-month follow-up (T_3) and at 18-month follow-up (T_4) .

Design and contents

ENTREN Programme (experimental)

This intervention consists in a total of 12 biweekly sessions: 9 sessions of 2-hr only for children, with a further three 3-hr sessions attended by both families and children together: nutrition, physical activity sessions, and a closing event session. Los contenidos

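### The SAP names two group-by-time models without saying which decides and gives no missing-data rule; a completers-only reading would keep about 192 of 240 children and could bias the arm comparison

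*SAP*

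**What the plan says.** The Protocol (Participants and Recruitment Procedure) plans 240 children in three randomised arms and states: "The dropout rate is expected to be 20" per cent. That figure is not split by arm or visit, and the text does not say whether 240 is counted before or after it. Assessments run from T0 (baseline) to T4 (18 months). Hypothesis (a) reads: "There will be significant differences in the adherence to treatment, being higher in the ENTREN-F group".

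The SAP gives the comparison model in two consecutive sentences. The first is "To carry out the comparisons, two-way analysis of covariance (ENTREN-F, ENTREN, Control Group) and time (T0,T1, T2 and T3) will be used". The second is "Mixed model repeated measures analyses of covariance models tested whether intervention effects varied for each type of group". Neither names a covariate, an estimation method or a covariance structure, and nothing says which of the two models decides. On effect size the SAP says: "Finally, the effect size will be measured using partial eta squared". BMI change by group is assigned separately to a Kruskal-Wallis test. The software is SPSS 26.0, with no procedure named.

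The supplied text contains no analysis population, intention-to-treat statement, missing-data rule, missingness assumption or sensitivity analysis. Part of the SAP was not available, so these absences are judged on the supplied text only.

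**The concern.** The two named models can treat a child with a missed visit differently. A classical repeated-measures ANCOVA works on one row per child and drops any child with a gap. A likelihood mixed model keeps the visits that were recorded. With one child in five expected to leave, the choice affects both the sample size and the estimate, and as written it can be made after the data are seen.

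Several details lean towards the classical model: T0 is a level of the time factor, no covariance structure is given, and partial eta squared is the natural output of a sums-of-squares decomposition. If completers alone are analysed, the groups compared are no longer the groups randomised. The arm difference is then biased if leaving the study differs by arm and is related to response.

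**Working it through.** **1. The planned number.** The 240 cannot be reproduced, because the supplied documents give no target effect, SD, power or primary endpoint. The dropout arithmetic does not help: 192 / (1 − 0.20) = 240 and 200 × 1.20 = 240 both fit.

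**2. Sample kept under a completers-only reading.** 240 × (1 − 0.20) = 192, or 64 per arm if allocation is 1:1:1 (assumed; the ratio is not stated). This takes 20% as the total dropout over the visits analysed.

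**3. Precision.** The detectable pairwise difference at 80% power, two-sided 5%, is (1.960 + 0.842) × √(2/n) in SD units:
- n = 80 per arm: 0.44 SD
- n = 64 per arm: 0.50 SD
- with alpha split over three pairs: 0.51 and 0.57 SD

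These figures are for a single visit without covariate adjustment.

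**4. Bias.** This was simulated with 400,000 children per arm, no true effect, visits T0 to T3, and permanent dropout after T1 or T2. Where dropout is outcome-related, it is more likely after a poor earlier change from T0. Entries are the ENTREN-F minus control difference in change from T0 to T3, in SD units, for an outcome where lower is better. The two values in a cell are for within-child correlation 0.70 and 0.85. The all-available-data column uses sequential regression within arm as a stand-in for a likelihood mixed model. Arm-specific rates, mechanism and correlation are assumptions; the documents give only 20% overall.

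| Dropout by T3 (ENTREN-F/ENTREN/control) | Log-odds of leaving per SD of poor change | Completers only | All available data |
|---|---|---|---|
| 20/20/20% | 0 | 0.001, −0.001 | 0.001, −0.001 |
| 10/20/30% | 0 | −0.003, −0.001 | −0.002, −0.001 |
| 20/20/20% | 1.5 | 0.001, 0.002 | 0.001, 0.001 |
| 10/20/30% | 0.75 | 0.050, 0.024 | 0.002, 0.000 |
| 10/20/30% | 1.5 | 0.082, 0.043 | 0.003, −0.001 |
| 10/20/30% | 3 | 0.105, 0.065 | −0.001, −0.001 |
| 15/20/25% | 1.5 | 0.038, 0.022 | −0.002, 0.000 |

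Unequal dropout alone gives no bias, and neither does outcome-related dropout of the same size and mechanism in every arm. Bias appears when dropout both differs by arm and depends on earlier outcome: 0.02 to 0.11 SD at 10/20/30%, and 0.02 to 0.04 SD at 15/20/25%. The sign flatters control, because more of its poor responders are removed. A true ENTREN-F benefit would therefore be pulled towards zero.

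**5. Second simulation.** This used 80 per arm, a true difference of 0.4 SD, correlation 0.6 to 0.8, and 10% against 30% dropout among poorer responders. The completer bias was 0.036 to 0.121 SD towards zero, that is 0.036/0.4 = 9% to 0.121/0.4 = 30% of the effect. The all-available-data bias was at most 0.006 SD. If only ENTREN-F dropout was response-related, the sign reversed, with 0.028 to 0.047 SD in favour of ENTREN-F.

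**6. BMI change.** A change score needs both visits. Without imputation, the Kruskal-Wallis test leaves out any child who lacks the later visit, whichever group-by-time model is meant.

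**The case against.** A reader might infer that the plan keeps only children with every visit and that this biases the arm comparison. The documents do not support that as fact, for four reasons.

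- Neither document mentions completers or listwise deletion, and the second SAP model sentence can describe a likelihood model that keeps incomplete records.
- Partial eta squared can be computed from any F statistic, as F·df1 / (F·df1 + df2), so it does not prove a classical decomposition.
- The two-way ANCOVA could also be run on one row per visit. That drops missing rows, not whole children.
- Hypothesis (a) concerns adherence to treatment. A child may miss sessions and still be measured.

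All four stand, and they limit the point to what the plan permits. They do not remove it. The row-per-visit reading ignores the correlation between visits of the same child, so the two-way ANCOVA is inferior under either literal reading. Differential, response-related loss is also plausible on the Protocol's own account. Its Background section moves directly from adherence to predictors of dropout, lists low motivation among them, and then names parental motivation as a predictor of treatment effect. That loss of outcome data follows remains an assumption.

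The size also depends on chosen arm-specific rates, and the main scenario shrinks the effect instead of creating one. Nothing in the documents supports the mechanism that reverses the sign.

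**Conclusion.** The point holds as a conditional one. The supplied SAP leaves two overlapping models in place for the same comparisons, with no analysis set and no missing-data rule. Its wording points to a completers-only analysis without establishing it.

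On that reading about 192 of 240 children remain, and the detectable pairwise difference rises from 0.44 to 0.50 SD. Bias of roughly 0.02 to 0.11 SD, mostly towards zero, arises only if dropout differs by arm (10/20/30% assumed) and relates to earlier response; at 15/20/25% it is 0.02 to 0.04 SD. If dropout is unrelated to outcome, or alike in size and mechanism across arms, the bias is about zero. The near-absence of bias in the likelihood analysis rests on data being missing at random.

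**What to change.** Delete the two-way ANCOVA and name one decisive model: a REML mixed model including all randomised children in their allocated arm and all available post-baseline visits. Fixed effects are arm, visit and arm-by-visit, with the T0 value as covariate and an unstructured visit covariance. List the visits explicitly, because the SAP sentence stops at T3 while the Protocol schedules T4. Report arm differences with 95% CI at each visit.

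State the missing-at-random assumption, and report by arm how many children have no post-baseline visit, since they add no information to this model. State whether the model also replaces the Kruskal-Wallis test for BMI change. Add one sensitivity analysis for data not missing at random, such as a delta shift applied to dropouts.

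The cost is SAP wording and a different procedure in the same software. Partial eta squared is no longer direct output, and the missingness assumption has to be made openly. The model does not recover all the precision lost to dropout.

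### The SAP makes pre-intervention T0 a level of the time factor and names neither a baseline covariate nor the treatment contrast; if the unadjusted group main effect is the test, it estimates only 0.75 of the post-baseline difference

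*SAP*

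**What the plan says.** The Statistical Analysis Plan specifies a two-way analysis of covariance in which group, with the three arms as levels, "and time (T0,T1, T2 and T3) will be used". It then describes mixed-model repeated-measures analyses of covariance that look at whether intervention effects differ by group. No covariate is named for either analysis. The only term tied to follow-up testing is the main effect of time, which leads to Bonferroni pairwise comparisons. Neither the group main effect nor the group-by-time interaction is named as the treatment test. BMI change over time by group has its own Kruskal-Wallis test.

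The protocol (Participants and Recruitment Procedure) places T0 "at baseline prior to the intervention (T_0" and lists T1 at the end of the intervention and T2, T3 and T4 at 6, 12 and 18 months. It also says that "Participants were randomly assigned to either" of the two programmes or the control group. T4 does not appear in the SAP's time factor.

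**The concern.** The comparison between arms is the main objective of the trial. A visit made before treatment carries no information about the treatment effect as an outcome, but much information as a baseline. Used as one of four equally weighted outcome visits in a group main effect, it pulls the estimate towards zero. Used as a covariate, it removes between-child variation.

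The SAP does not say which use is meant. An analyst following the text could report a group main effect over T0 to T3, a 6-df interaction, or a model in which T0 is on both sides. These answer different questions with very different power, although every child who enters the analysis is meant to have a T0 value already.

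**Working it through.** **Inputs from the documents**
- Four time levels including T0 (SAP); T0 before the intervention, three randomised arms (protocol).
- 240 children and 20% expected dropout (protocol): 240 × 0.80 = 192 completers.
- Significance level 0.05 (SAP: "The value P<0.05 was considered as a significant difference").

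**Assumptions (not in the documents)**
- 1:1:1 allocation, so 192 / 3 = 64 completers per arm; two-sided test.
- Difference d = 0.4 SD, the same at T1, T2 and T3; SD 1 at each visit.
- Equal correlation ρ between all visits, 0.5 to 0.8; complete data; no clustering.

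The plan's own figure of 240 cannot be reproduced, because no effect size, SD or power is given.

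**Step 1: what the group main effect estimates.** With equal visit weights and zero expected difference at T0, it is (0 + d1 + d2 + d3)/4 = 0.75 × (d1 + d2 + d3)/3. The factor 0.75 holds whatever the time profile.

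**Step 2: pairwise power (non-central t, 64 per arm).**
- Unadjusted mean of T0–T3: effect 0.75d = 0.30, variance (1 + 3ρ)/4.
- Mean of T1–T3 with T0 as covariate: effect d = 0.40, variance (1 + 2ρ)/3 − ρ².
- Mean of T1–T3 minus T0 (a 1-df group-by-time contrast): effect d = 0.40, variance (1 + 2ρ)/3 + 1 − 2ρ.

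At ρ = 0.5 the variances are 0.625, 0.417 and 0.667. Dividing each effect by √(2 × variance/64) gives non-centralities of 2.15, 3.51 and 2.77.

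| ρ | T0–T3 group main effect | T1–T3, T0 as covariate | T1–T3 minus T0 |
|---|---|---|---|
| 0.5 | 56.8% | 93.6% | 79% |
| 0.6 | 52.1% | 95.7% | 87% |
| 0.7 | 48.1% | 98.1% | 94% |
| 0.8 | 44.7% | 99.7% | 99% |

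**Step 3: three-arm tests (non-central F, both active arms differing from control by d).** The between-arm sum of squares is 64 × d² × 2/3 = 64 × 0.16 × 2/3 = 6.83.
- Group-by-time, 6 and 567 df: the effect profile (0, 1, 1, 1) has squared deviations 0.5625 + 3 × 0.0625 = 0.75, so the non-centrality is 6.83 × 0.75/(1 − ρ).
- Baseline-adjusted T1–T3 mean, 2 and 188 df: the non-centrality is 6.83/[(1 + 2ρ)/3 − ρ²].

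| ρ | Group-by-time, 6 df | Baseline-adjusted, 2 df |
|---|---|---|
| 0.5 | 65% | 96% |
| 0.6 | 76% | 97% |
| 0.7 | 89% | 99% |
| 0.8 | 98% | over 99% |

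**Step 4: T0 as both covariate and outcome level.** The T0 residual is then zero. The four-visit mean has effect 0.75d and residual SD 0.75 times that of the T1–T3 mean. The factor cancels in the test statistic, so power and partial eta squared for the group term equal those of the baseline-adjusted analysis. The reported mean difference is 0.75 × 0.40 = 0.30 SD instead of 0.40 SD.

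**The case against.** The strongest reply is that the SAP never says the group main effect is the treatment test. The mixed-model sentence reads naturally as a group-by-time question, and the protocol's hypotheses are about improvement after the intervention and stability at follow-up. In a group-by-time test T0 is the reference and nothing is diluted. This stands, so the 0.75 factor can only be stated conditionally. But the SAP does not name the interaction as the treatment test either, and the only effect it does name for follow-up, time, does not compare arms. The 6-df test also costs power at moderate correlation.

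A reader might infer more than the documents support, in four ways:
- *That T0 is used as an outcome instead of as a covariate.* The text calls the model an analysis of covariance without naming the covariate, so baseline adjustment is neither stated nor excluded.
- *That power is lost under every reading.* It is not if T0 is both covariate and outcome level (Step 4), and the between-arm test there does not depend on sphericity.
- *That T0 in the outcome vector is an error in itself.* A longitudinal model with baseline means constrained equal across arms is as efficient as covariate adjustment with complete data. The SAP states no such constraint.
- *That BMI is affected.* Its Kruskal-Wallis test is on changes and lies outside this point.

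**Conclusion.** The point holds as a conditional one, for the outcomes analysed by the two-way or mixed model. T0 is a level of the time factor, and both the covariate and the treatment contrast are left open. The consequence depends on how the gap is filled:
- **Unadjusted group main effect:** a quarter of the mean post-baseline difference is lost from the estimate, and the power loss is large throughout the range examined.
- **Group-by-time interaction:** no dilution. The loss is real at moderate correlation (about 31 percentage points at ρ = 0.5, 96 − 65) and nearly vanishes at ρ = 0.8.
- **T0 on both sides:** no loss of power, but an understated group difference.

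The 0.75 factor needs only randomisation and equal visit weights. Every power figure rests on the assumed d, ρ, allocation, equal-correlation structure and complete data. They show the ordering and rough size, not the trial's actual power. Because a better use of data already collected is available at almost no cost, the SAP should be changed.

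**What to change.** For the outcomes analysed by the two-way or mixed model, state in the SAP that:
1. the outcomes are the post-baseline visits only (T1 to T3, and T4 if it is meant to be analysed);
2. the covariate is the T0 value of the same variable, with its interaction with visit;
3. the treatment test is the arm contrast at each post-baseline visit and averaged over those visits.

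With complete data, an equivalent is to keep T0 in the outcome vector and constrain the baseline means to be equal across arms. The SAP should then say so and name the same contrasts.

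The cost is a few sentences in the SAP and a respecified model. It needs no new data or visits and no change in sample size.

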Another important aspect in childhood obesity interventions is their intensity and duration. In this sense, medium-high intensities and longer durations have been associated with greater efficacy (Whitlock, O'Connor, Williams, Beil, & Lutz, 2010). Specifically, Kitzmann et al.'s (2010) review noted that with an intervention duration of around four months, the results obtained were as effective as with more extensive interventions.

Adherence to treatment is another crucial aspect in the treatment of obesity. There are studies that define which variables predict the drop-out of treatment, such as the bad relationship between parents and the child, the lack of time and motivation, the coincidence with other academic activities, the high level of family stressors, and the distance between the home and the center where the intervention is being carried out (Brennan, Walkley, & Wilks, 2012; Moroshko, 2011; Braet, Jeannin, Mels, Moens, & Van Winckel, 2010; Barlow & Ohlemeyer, 2006).

Other relevant factors that predict greater treatment effectiveness are variables such as age and gender (Moens et al., 2010; Goossens, Braet, Van Vlierberghe, & Mels, 2009), placing adolescence as a more difficult stage in which to achieve changes. Other variables include psychological problems during childhood (Moens et al., 2010; Epstein, Klein, & Wisniewski, 1994) and the degree of parental motivation (Gunnarsdottir et al., 2011; Braet et al., 2010; Moens, Braet, & Van Winckel, 2010; Braet, 2006). Despite taking into account all the previously described variables, the vast majority of treatments have focused on long-term weight reduction as the sole objective of intervention, leaving aside all these psychological and family correlates that maintain the problem.

Objetive

The main objective is to examine the effectiveness of the intervention program 'ENTREN-F' (intervention for children plus family intervention) on anthropometrics, behavior, psychological and family factors, from a multidisciplinary perspective, compared with another group participating in the same program 'ENTREN' (intervention for children without family intervention) and with a control group (usual treatment) among Spanish children with over-weight and obesity. Finally, the second aim was to evaluate whether the changes were maintained 6, 12 and 18 months after the end of the intervention.

Hyphotesis

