de las sesiones con los niños se basan en una perspectiva cognitivo-conductual e incluyen estrategias de la entrevista motivacional. El objetivo de las sesiones con los niños es trabajar la conciencia del problema, la motivación al cambio, el concepto de salud, la regulación emocional, las habilidades sociales y autoestima. One 2-hr sesión at 6, 12 and 18-month follow-up was provided to refresh skills, their physical activity, and nutritional behaviours.

ENTREN-F Programme (experimental)

ENTREN-F has the same children's intervention than ENTREN. It has extra 6 2-hr sessions to work on family environment and communication, plus three 2-hr sessions attended by both families and children together. One 2-hr sesión at 6, 12 and 18-month follow-up was provided to refresh skills, their physical activity, and nutritional behaviours.

Control Group Programme

The intervention of this group consists in usual treatment in Primary Care provided by Endocrinology Services. 3 monthly face-to-face consultations and continous online monitoring are provided to these families, oriented to promote healthy habits of nutrition and physical activity for 6 months. It works from an exclusively behavioral perspective. We used a *token economy*, a system of contingency management based on the systematic reinforcement of target behavior.

Instruments

• Anthropometric variables

Nurses measured children and parents: height, weight, waist circumference and middle arm circumference. Mother and children's Body mass index (BMI) has been calculated. Participating children's BMI Z-scores was calculated according to the age and specific sex, according to the median and standard deviation, based on the data collected in the Growth Tables of Orbegozo Foundation (Sobradillo et al., 2004).

• Lifestyle habits

Actigraph, model GT3X. The Actigraph (Actigraph TM, LLC, Fort Walton Beach, FL, EE.UU) is a small and lightweight triaxial activity monitor/accelerometer (4,6 x 3,3 x 1,5

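### The SAP's time factor stops at T3 (12 months), so the 18-month part of the second aim and of hypothesis (e) has no prespecified test in the SAP text reviewed

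*SAP*

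**What the plan says.** The protocol's Participants and Recruitment Procedure section fixes the visit labels: T0 at baseline, T1 at the end of the intervention, T2 at 6 months, and then assessments "at 12-month follow-up (T_3) and at 18-month follow-up (T_4"). The second aim, under the objective heading, is to "evaluate whether the changes were maintained 6, 12 and 18 months after the end of the intervention". Hypothesis (e) reads "The significant changes produced will remain stable at the 6, 12 and 18-month follow-up in the ENTREN-F group". The Design and contents section plans contact at 18 months in both experimental programmes: a session "at 6, 12 and 18-month follow-up was provided to refresh skills".

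The SAP has four relevant statements:

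- The group-by-time comparison: "time (T0,T1, T2 and T3) will be used".
- The BMI analysis: "Participant BMI changes over time by group will be measured using a Kruskal-Wallis test". No visits are named.
- A mixed-model repeated-measures sentence about whether intervention effects differ by group. No visits are named.
- A post hoc step, run after significance in the global comparisons: "pairwise comparisons following asignificant main effect of time (post hoc Bonferroni test").

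Neither T4 nor 18 months appears in the SAP text reviewed, and no reason is given for leaving that visit out.

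**The concern.** Two things do not match the protocol.

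First, the listed time factor omits a visit that the second aim and hypothesis (e) both require. Followed as written, the model yields no estimate or test at 18 months. The longest-term result would then be left out, or would rest on an analysis that could be chosen after the data are seen.

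Second, hypothesis (e) is about one arm. A main effect of time pools the three arms, so it can hide a relapse in ENTREN-F or show one that occurred elsewhere. No contrast from T1 to a follow-up visit within ENTREN-F is named, and this affects T2 and T3 as well as T4. The pairwise step also runs only after a significant result, whereas the hypothesis predicts stability. A non-significant difference would not by itself show that the gains were kept.

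**Working it through.** **Visit coverage.** The plan states no figure to reproduce here, so the check is a match of labels.

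| Visit | Timing (protocol) | In second aim and hypothesis (e) | In SAP time factor |
|---|---|---|---|
| T0 | baseline | – | yes |
| T1 | end of intervention | reference for maintenance | yes |
| T2 | 6 months | yes | yes |
| T3 | 12 months | yes | yes |
| T4 | 18 months | yes | no |

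The protocol defines T3 as 12 months, so the SAP's T3 cannot be read as the 18-month visit. The gap is 1 of 4 post-baseline visits, 1 of 3 maintenance time points, and the last 18 − 12 = 6 of 18 follow-up months.

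**Whether another SAP sentence fills the gap.** The Kruskal-Wallis sentence covers BMI only. It compares groups, so even with T4 included it would not test stability within one arm. The mixed-model sentence could be run with T4 but does not say so. Neither excludes T4 and neither commits to it.

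**What the main effect of time measures.** Let the changes from T1 to a follow-up visit be d(F), d(E) and d(C) in ENTREN-F, ENTREN and control. With equal arm weights, the main-effect contrast is [d(F) + d(E) + d(C)]/3. If only ENTREN-F changes, by d, it is (d + 0 + 0)/3 = d/3. Zero change in the other arms is an illustration. In general the contrast mixes all three arms.

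**Effect of adding T4.** With k visits and 3 groups:

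| Quantity | Formula | k = 4 | k = 5 |
|---|---|---|---|
| Time df | k − 1 | 3 | 4 |
| Group-by-time df | 2(k − 1) | 6 | 8 |
| Pairs of visits | k(k − 1)/2 | 6 | 10 |
| Bonferroni level, all pairs | 0.05/pairs | 0.0083 | 0.005 |

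If only T1–T2, T1–T3 and T1–T4 are tested, the level is 0.05/3 = 0.0167.

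**Precision of one within-ENTREN-F contrast.** The protocol gives 240 children, three arms and 20% expected dropout. Assuming equal allocation and equal dropout across arms, ENTREN-F has 240/3 × 0.8 = 64 children. With the same SD at both visits and between-visit correlation ρ (assumed; neither document gives it), the 95% half-width in SD units is 1.96 × √(2(1 − ρ)/64):

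| ρ | Half-width (SD) |
|---|---|
| 0.5 | 0.245 |
| 0.7 | 0.190 |
| 0.8 | 0.155 |
| 0.9 | 0.110 |
| 0.95 | 0.077 |

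These intervals are not adjusted for multiplicity. At the 0.0167 level (z about 2.39), the half-widths for ρ = 0.7 to 0.95 become about 0.23, 0.19, 0.13 and 0.09 SD.

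**The case against.** The strongest reply is that this is one missing visit label for a secondary aim. The main between-group comparison is untouched, two of the three maintenance visits are in the model, and the mixed-model and Kruskal-Wallis sentences carry no visit restriction, so T4 may always have been intended. That limits the scope of the defect but does not remove it: a sentence that could include T4, beside an explicit list that omits it, does not prespecify a test. The claim is confined to the SAP text reviewed. That an analysis would be picked after seeing the data is a risk the wording leaves open, not something the documents show.

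A second reply is that the missing ENTREN-F contrast is a separate matter, and that the SAP's trigger for pairwise tests might include the group-by-time term. The wording is loose enough for that reading. Still, the only post hoc step named is for time, and hypothesis (e) cannot be answered at any follow-up visit without a contrast in that arm.

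A third is that the precision figures are illustrative and that high correlations are optimistic for the questionnaires. The protocol reports an alpha of 0.68 for the child depression inventory and a test-retest r of 0.74 for the perfectionism scale. This is fair, and it is why ρ = 0.5 is shown. The figures describe the proposed contrasts; they do not measure the harm from omitting T4.

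**Conclusion.** The concern holds. The protocol promises an answer at 18 months and the listed SAP model cannot give one. No other sentence in the SAP text reviewed commits to it. This is an inconsistency between protocol and SAP, not just missing detail, and it should be corrected before analysis. The damage is limited to the second aim and hypothesis (e).

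The visit mismatch rests on no assumption. The d/3 figure assumes equal weights and no change in the other two arms. The half-widths, 0.08 to 0.25 SD over the range shown, assume 64 children in ENTREN-F, equal SDs and the stated correlations.

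**What to change.** 1. Change the SAP's time factor to T0, T1, T2, T3 and T4.
2. Name the within-ENTREN-F changes from T1 to T2, T1 to T3 and T1 to T4, estimated from the group-by-time model, as the analysis of hypothesis (e), each with a 95% confidence interval. Do not make them depend on a significant main effect of time.
3. Judge maintenance from the estimated loss and its interval, not from p > 0.05 alone. The documents give no margin for acceptable loss, so if a yes-or-no conclusion is wanted, the team must set one in advance.
4. State the Bonferroni family: all pairs of visits, or the three named contrasts only.
5. If T4 is to be analysed separately, say so and name the method. If 18-month data will not be analysed, amend the second aim and hypothesis (e) to match.

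The cost is one corrected line and a sentence or two. The protocol already schedules the visit, so no new data are needed. The statistical price is the stricter all-pairs level (0.005 instead of 0.0083), which is avoided by limiting tests to the three named contrasts (0.0167).
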